## **7.7 Calculation or derivation of tumour response variables**

The preliminary anti-tumour activity of MEDI-573 will be assessed based on the following variables: objective response rate (ORR), time to response (TTR), duration of response (DR), time to progression (TTP), and progression-free survival (PFS).

Categorisation of overall objective tumour response assessment will be based on the RECIST ver1.1: complete response (CR), partial response (PR), stable disease (SD) and progressive disease (PD) for all subjects with measurable disease at entry.

Response will be calculated in comparison to the baseline tumour measurements obtained before starting study treatment. Progression will be calculated in comparison to when the tumour burden was at a minimum (ie, smallest sum of diameters previously recorded since starting the study).

For patients that have measurable disease at entry, overall response at entry will be determined programmatically by the measurement of the target lesion, the response of the non-target

Date

lesion and the presence of new lesion according to the RECIST ver1.1. The subject's best overall response is the best response recorded from the start of the study treatment.

In the case of SD, measurements should have met the SD criteria at least once after the study start. To be assigned a status of partial response or complete response, changes in tumour assessments should be confirmed no less than 4 weeks after the criteria for response were first met.

For subjects that only have non-measurable disease at study entry, RECIST will be used. Visit response will be assigned programmatically and summarised separately.

Percentage change in tumour size will be determined by the percentage change in the sum of the longest diameters of target lesions.

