### **3.1 Overall study design and flow chart**

#### **Study Design**

This is a Phase 1, open-label, single-arm, dose-escalation study to evaluate the safety, tolerability, and pharmacokinetics of MEDI-573 in Japanese adult patients with advanced solid tumours refractory to standard therapy or for which no standard therapy exists.

The study will be conducted at one site in Japan.

Subjects are considered evaluable if they receive 3 doses of MEDI-573 (Cohorts 1 and 2) or 1 dose of MEDI-573 (Cohort 3) during cycle 1 and are followed for 21 days from the date of first dose (one cycle) or they discontinue MEDI-573 due to dose-limiting toxicities (DLTs). Each cohort will include 3 to 6 evaluable subjects and a total of 9 to 18 evaluable subjects will be evaluated during the study.

MEDI-573 will be administered once every 7 days (on Days 1, 8, and 15 of each 21-day treatment cycle) as a 60-minute IV infusion in Cohorts 1 and 2 and once every 21 days (Day 1 of each 21-day treatment cycle) as a 90-minute IV infusion in Cohort 3 until unacceptable toxicity, documentation of disease progression, or other reasons for subject withdrawal. Intra-subject dose escalation will not be allowed. On 2nd Cycle and beyond, continuation, interruption or permanent discontinuation of treatment will be decided based on the criteria specified in section 5.1.8. Subjects will be considered to have completed a cycle only when they have received all the specified doses at each cycle, and subjects who do not complete a cycle will discontinue the treatment and not move on to the next cycle. Rules for interruption or discontinuation of MEDI-573 in individual subjects are described in Section 5.4.1. Rules for interruption or discontinuation of MEDI-573 and study entry are described in Section 5.4.2.

Dose escalation will follow a standard 3+3 design. Rules for dose escalation are described in Section 5.1.3.

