#### **Subject Evaluation/Follow-up**

A schedule of screening, treatment visit and follow-up visit procedures are presented in [Table 5](#) (Cohorts 1 and 2) and [Table 9](#) (Cohort 3).

The details of the evaluations are shown in Section 6.1.

[figure not shown]
AEs and SAEs during the study will be assessed from the time the subject provides the consent through 30 days after the last dose of MEDI-573. AEs will be graded according to the National Cancer Institute Common Terminology Criteria for Adverse Events Version 4.0 (NCI CTCAE V4.0). In addition, disease evaluations (including computerised tomography (CT) or magnetic resonance imaging (MRI) scans), focused physical examination, and world health organization (WHO) performance status will be performed after every 2 cycles of treatment until documentation of disease progression or initiation of alternative anticancer therapy. For subjects who discontinue treatment due to reasons other than disease progression or initiation

Date

of alternative anticancer therapy, disease evaluations will be performed at 3 months after the last dose of MEDI-573. Subjects will be evaluated for disease response using Response Evaluation Criteria in Solid Tumours (RECIST ver 1.1; [Eisenhauera et al 2009](#)).

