**Table 5 Study plan (Cohorts 1 and 2)**

Assessment	Screen	Cycle 1					Cycle 2 and Beyond			End of Treatment d	Follow-up		Details in
		Day 1	Day 2	Day 3	Day 8	Day 15	Day 1	Day 8	Day 15		30 days after the last dose	3 months after the last dose	
Allowance (days)	- 28 - 1	—	—	—	—	—	±2	±2	±2		+3	±14	
Written Informed Consent	X						X a						Appendix D
Verify Eligibility Criteria	X	X											4.1, 4.2
Medical History	X												6.3
Pregnancy test b	X	X					X				X		6.3.5
WHO Performance Status	X	X					X			X	X	X c	6.3.2
Physical Examination	X	X					X			X	X	X c	6.3.2
Height	X												6.3.2
Weight	X	X					X			X	X		5.1.2
Vital Signs	X	X		X	X	X	X	X	X	X	X		6.3.3
ECG	X	X					X			X	X		6.3.4
Haematology/ Clinical Chemistry	X	X		X	X	X	X	X	X	X	X		6.3.5
Urinalysis	X	X			X	X	X	X	X	X	X		6.3.5
Tumour assessment (CT or MRI Scans)	X						X c			X		X c	6.9.1
Tumour marker	X						X c			X		X c	6.9.2
PK f		X	X	X	X	X	X	X g	X g	X	X		6.5
Anti-MEDI-573 Antibodies		X					X				X	X	6.5.3
Blood Biomarker Analysis		X	X	X	X	X	X	X	X	X	X		6.7

Date

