**Table 5 Study plan (Cohorts 1 and 2)**

Assessment	Screen	Cycle 1					Cycle 2 and Beyond			End of Treatment d	Follow-up		Details in
		Day 1	Day 2	Day 3	Day 8	Day 15	Day 1	Day 8	Day 15		30 days after the last dose	3 months after the last dose	
Allowance (days)	- 28 - 1	—	—	—	—	—	±2	±2	±2		+3	±14	
Insulin/GH		X	X	X	X	X	X	X	X	X	X		6.7
Archived Tumour Sample (Optional) h	X												6.7
Tumour Biopsy (Optional) i	X												6.7
MEDI-573 Administration		X			X	X	X	X	X				5
AE Assessment	X	X	X	X	X	X	X	X	X	X	X		6.4
Concomitant Medications	X	X	X	X	X	X	X	X	X	X	X		4.3.1

a Only cycle 2, if subject would like to continue the study.

b All female subjects of child-bearing must be tested. Serum samples will be used at screening only and urine samples will be used at other visits.

c Tumour assessments will be done at odd cycles only and be required before odd treatment starts.

d All possible measures will be performed at end of treatment.

e Subjects who discontinue the study treatment for reasons other than disease progression or initiation of alternative anticancer therapy will undergo Tumour assessment 3 months after the last dose of MEDI-573.

f PK samples will be collected according to [Table 13](#).

g Only cycle 2.

h If an archived tumour sample is available and the subject provides consent for its use; collect and ship per instructions in the Laboratory Manual.

i If the subject provides consent for its use and the samples are collected in a clinical routine at pre- and post (from day 15 to day 21 in cycle 1)- MEDI-573 treatment, the samples will be shipped per instructions in the Laboratory Manual.

Date

**Table 6 Time window for vital signs (body temperature, respiratory rate, blood pressure and pulse) (Cycle 1, Cohorts 1 and 2)**

Time point	Screen	Day 1							Day 3	Day 8	Day 15
		Pre-dose a	15 min post initiation of infusion	30 min post initiation of infusion	45 min post initiation of infusion	End of infusion	30 min post infusion	60 min post infusion			
Allowance	-	-	±5 min	±5 min	±5 min	±5 min	±5 min	±5 min	-	b	b

a Measurement should be done on the day of the first infusion of MEDI-573.

b Measurement should be done at the same time points as Day 1.

**Table 7 Time window for vital signs (body temperature, respiratory rate, blood pressure and pulse) (Cycle 2 and Beyond, Cohorts 1 and 2)**

Time point	Day 1							Day 8	Day 15	End of Treatment	30 days after the last dose

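### A best overall response of stable disease can rest on one scan in the first weeks, because Section 7.7 sets no minimum time on study for SD

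*Protocol*

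**What the plan says.** **Response rules (Protocol Section 7.7).** For SD, "measurements should have met the SD criteria at least once after the study start". For CR and PR, "changes in tumour assessments should be confirmed no less than 4 weeks after the criteria for response were first met". For the summary across visits, "The subject's best overall response is the best response recorded from the start of the study treatment".

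**Scan schedule.** Section 3.1 says disease evaluations "will be performed after every 2 cycles of treatment until documentation of disease progression". Footnote c of Tables 5 and 9 says "Tumour assessments will be done at odd cycles only and be required before odd treatment starts". Both tables also mark the tumour assessment in the End of Treatment column, with no condition on time on study. That column carries footnote d: "All possible measures will be performed at end of treatment". Under Section 6.9.1, subjects who stop for a reason other than progression or a new anticancer therapy have a further assessment 3 months after the last dose.

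**Who is analysed.** The tumour response set in Table 20 takes any subject with at least one dose and at least one tumour assessment after treatment began. It sets no timing condition.

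**Which variables are listed.** Section 7.7 names ORR, TTR, DR, TTP and PFS. The heading of Section 7.7.1 mentions disease control, but the text below it defines no such rate.

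**The concern.** Section 7.7 sets a time requirement for the two response categories and none for SD. The first scheduled on-treatment scan falls about 6 weeks after first dose, but the end-of-treatment scan can fall much earlier.

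The design makes early stopping foreseeable. Subjects who do not complete a cycle discontinue (Section 3.1), a DLT is a listed reason for stopping (Section 5.4.1), and entry to Cycle 2 needs separate written consent (Section 5.1.9). A scan 1 to 3 weeks after first dose gives a tumour little time to grow, so a finding of no progression says little about whether the drug stabilised the disease.

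At stake is the meaning of SD in a best-response table. A subject who left in the first weeks, perhaps for toxicity, would appear in the same row as a subject whose disease was stable at the planned assessment.

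**Working it through.** No figure in the protocol depends on this rule, so there is none to reproduce. The check has three parts: when scans fall, how the written rule classifies an early stopper, and what one such subject weighs.

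**1. Timing of scans**
- Cycle length is 21 days: dosing in Cohorts 1 and 2 is "on Days 1, 8, and 15 of each 21-day treatment cycle", and Cohort 3 is dosed every 21 days (Section 3.1).
- Cycle 3 Day 1 = 1 + 2 × 21 = Day 43, which is 6 weeks after first dose.
- With the visit allowances in Tables 5 and 9, that visit falls on Day 41–45 in Cohorts 1 and 2 (±2 days) and Day 43–45 in Cohort 3 (+2 days). Neither table gives a separate window for the scan, which must precede the dose.
- End-of-treatment scans on Days 8, 15 and 22 fall 1, 2 and 3 weeks after first dose. They are 43 − 8 = 35, 43 − 15 = 28 and 43 − 22 = 21 days before the first scheduled scan.

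**2. Classification under the written rule**

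Take a subject who stops in Cycle 1 and whose end-of-treatment scan shows neither response nor progression.
- Table 20: one dose and one later scan, so the subject is in the tumour response set.
- Section 7.7: the SD criteria have been met once, so SD is recorded.
- Section 7.7: best overall response is the best recorded, so it is SD. If the 3-month scan then shows PD, SD remains the better of the two and stands.
- No other section sets a minimum time for SD or classes such a scan as not evaluable.

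**3. Weight of one such subject**

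The weight is 1/n, where n is the number in the tumour response set. The protocol plans 3 to 6 evaluable subjects in each of three cohorts, so 3 × 3 = 9 to 3 × 6 = 18 in total. Those are counts of DLT-evaluable subjects. A non-evaluable subject is replaced (Section 5.4.1) and so adds one to n.

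| Case | Within a cohort | Whole study |
|---|---|---|
| DLT-evaluable (for example, stopped for a DLT) | 1/6 = 16.7% to 1/3 = 33.3% | 1/18 = 5.6% to 1/9 = 11.1% |
| Not evaluable and replaced (for example, left by choice before the third weekly dose) | 1/7 = 14.3% to 1/4 = 25.0% | 1/19 = 5.3% to 1/10 = 10.0% |

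These figures assume that every other subject also has a post-start scan and that at most one subject is replaced. Section 7.7 summarises subjects with only non-measurable disease separately, so restricting to measurable disease changes n again.

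**4. How likely it is**

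The protocol gives no rate of early stopping. As an assumption only, let 10–30% of subjects stop early, have the scan done and show no progression. The chance of at least one among n is 1 − (1 − p)^n:
- n = 9: 1 − 0.9^9 = 61% to 1 − 0.7^9 = 96%.
- n = 18: 1 − 0.9^18 = 85% to 1 − 0.7^18 = more than 99%.

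**The case against.** **No listed variable uses SD.** This is correct and limits the point. A reader might infer that early toxicity drop-outs would be credited as benefit in the efficacy endpoints. The documents do not support that. Such a subject is a non-responder for ORR, TTR and DR concern responders only, and TTP and PFS depend on progression or death. Progression at the 3-month scan is still captured in TTP and PFS. Nor does the plan define a disease control rate that would be inflated; only a section heading names disease control.

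**The end-of-treatment scan is not an absolute requirement.** This also stands. Footnote d asks for what is possible, so the misclassification needs an early stop, a scan actually done, and no progression on it.

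**This is a detail for the SAP, or is covered by RECIST 1.1.** This stands only in part. The SD sentence can be read as a minimum to which a SAP could add an interval without contradicting it. But Section 7.7 writes its own SD rule beside the RECIST citation, and nothing in the protocol adds an interval. Section 7.9 foresees a SAP only if one is needed. The point therefore concerns a rule the protocol states, not a missing detail.

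**The evaluable counts are the wrong denominator.** This is right for subjects who are replaced, which is why the working gives both cases.

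**Conclusion.** The point holds as a minor defect of definition. As written, Section 7.7 classes a subject with a single non-progressing scan 1 to 3 weeks after first dose as SD, and a later PD does not change that. The reach is confined to the descriptive SD category of best overall response and to any disease-control summary that might be built on it. The five listed anti-tumour variables, the primary safety endpoint and dose escalation are untouched.

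One such subject moves the SD proportion by about 17–33 percentage points in a cohort and 6–11 overall if DLT-evaluable, or by about 14–25 and 5–10 if replaced. These sizes rest on the planned cohort sizes, on all other subjects having a post-start scan, and on no restriction to measurable disease. How often it would happen cannot be derived from the protocol.

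**What to change.** Add to Section 7.7 that a best overall response of SD requires the SD criteria to be met at or after the first scheduled on-treatment assessment. That is the scan before Cycle 3 Day 1, nominally Day 43, and a scan window should be stated so that the rule can be programmed. Add that subjects whose only post-baseline scan is an earlier non-progression scan are reported as not evaluable for best response and kept in the denominator.

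Keeping them matters. With s subjects in SD out of n, reclassifying one gives (s − 1)/n. Dropping the subject would give (s − 1)/(n − 1), a different and less transparent change.

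A subject who also has the 3-month scan is then classified on that scan. Taking 3 months as about 90 days, even a subject dosed only on Day 1 and scanned 14 days early is assessed at about Day 1 + 90 − 14 = Day 77, after Day 43.

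The change needs no extra scan, visit or subject. Its only downside is that the reported SD proportion may be slightly less favourable.

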### **7.7.1 Objective response and disease control**

ORR is defined as the proportion of subjects with confirmed CR or confirmed PR according to RECIST ver1.1. Confirmed responses are those that persist on repeat imaging study  $\geq 4$  weeks after the initial documentation of response.

TTR will be measured from the start of treatment with MEDI-573 to the first documentation of objective response and will only be assessed in subjects who have achieved objective response.

DR will be defined as the duration from the first documentation of objective response to the first documented disease progression. DR will only be calculated for the subgroup of subjects with an objective response during the study period (until 3 months after the last dose).

TTP will be measured from the start of treatment with MEDI-573 until the documentation of disease progression during the study period (until 3 months after the last dose).

PFS will be measured from the start of treatment with MEDI-573 until the documentation of disease progression or death due to any cause, whichever occurs first during the study period (until 3 months after the last dose).

## **7.8 Description of analysis sets**

The analysis of data will be based on different subsets according to the purpose of the analysis. Throughout the safety results sections, erroneously treated subjects (eg, those assigned to receive dose A who actually received dose B, those who failed to meet the selection criteria) will be accounted for in the actual dose group received.

Analysis sets are presented in [Table 20](#).

The classification of subjects into analysis sets will be done at the clean file meeting prior to the database lock.

Date

**Table 20**                      **Analysis sets**

Analysis Set	Definition
Safety	All subjects who received at least 1 dose of MEDI-573.
MTD	All subjects who have received at least 1 full cycle of MEDI-573 and completed the safety follow-up through the DLT evaluation period, or who experienced a DLT.
PK	All subjects who received at least 1 dose of MEDI-573 and for whom an adequate PK profile has been obtained.
Pharmacodynamics	All subjects who received at least 1 dose of MEDI-573 with any post-pharmacodynamics data
Tumour response	All subjects who have received at least 1 dose of MEDI-573 and at least one tumour assessment after the initiation of MEDI-573.
Exploratory biomarkers	All subjects who received at least 1 dose of MEDI-573 and have biomarkers data.

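### Table 20 admits a subject to the tumour response set only after a post-baseline scan, so deaths before any scan can drop out of PFS and never-rescanned subjects out of the ORR denominator.

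*Protocol*

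**What the plan says.** Protocol Section 7.7 groups five measures as tumour response variables: ORR, TTR, DR, TTP and PFS. Section 7.7.1 gives the ORR definition: "ORR is defined as the proportion of subjects with confirmed CR or confirmed PR according to RECIST ver1.1". It does not say which subjects form the denominator. The same section runs PFS from the start of treatment "until the documentation of disease progression or death due to any cause, whichever occurs first during the study period", the study period ending 3 months after the last dose.

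Table 20 then gives the tumour response set: "All subjects who have received at least 1 dose of MEDI-573 and at least one tumour assessment after the initiation of MEDI-573". The Safety set in the same table needs only treatment: "All subjects who received at least 1 dose of MEDI-573". No other row concerns efficacy. The rule linking analyses to sets in Section 7.8 is general: "The analysis of data will be based on different subsets according to the purpose of the analysis".

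On scan timing, footnote c of Table 5 says "Tumour assessments will be done at odd cycles only and be required before odd treatment starts", and Table 9 has the same note for Cohort 3. Both tables also mark a tumour assessment at the end-of-treatment visit, with footnote d: "All possible measures will be performed at end of treatment". Section 6.9.1 adds a scan 3 months after the last dose for subjects who stopped for reasons other than progression or a new anticancer therapy.

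Section 7.9 treats missing data as missing, with no imputation.

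**The concern.** Membership of the set depends on something that happens after treatment starts: living and staying in the study long enough to be scanned. The subjects it leaves out are not a random sample. A subject who dies unscanned has had a PFS event as Section 7.7.1 defines it. A subject never scanned again cannot be a confirmed responder. Removing the first kind takes early events out of PFS; removing the second takes non-responders out of the ORR denominator. Both shifts flatter the drug.

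The set also sits badly with Section 6.9.1, which plans a response assessment for everyone with measurable or non-measurable disease at baseline. Inclusion criterion 6 requires a baseline lesion, so that covers every correctly enrolled subject. Because nothing is imputed, no rule in the protocol brings the omitted subjects back as non-responders.

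At stake is the reading of anti-tumour activity. Section 7.10.1 bases the main conclusions on secondary objectives on these data, and in cohorts of 3 to 6 one lost subject is visible.

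**Working it through.** **1. Planned size.** Section 3.1 states 9 to 18 evaluable subjects. Three cohorts of 3 to 6 give 3 × 3 = 9 and 3 × 6 = 18, so the figure reproduces. Non-evaluable withdrawals are replaced (Section 5.4.1), so the number treated can exceed this. There is no hypothesis test or power calculation to check.

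**2. First scheduled on-treatment scan.** Cycles last 21 days and the scan precedes Cycle 3 Day 1: 2 × 21 + 1 = nominal Day 43.

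**3. Who falls outside the set.**

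- Dies before any post-baseline scan: outside the set, but a PFS event under Section 7.7.1.
- Stops early and has an end-of-treatment or 3-month scan: inside the set.
- Stops early and is never scanned again (death, withdrawn consent, loss to follow-up, too ill for the end-of-treatment scan): outside the set, and a non-responder missing from the ORR denominator.

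**4. Effect on ORR.** Let n be the number treated, k the number never scanned and r the number of responders. All treated gives r/n; the Table 20 set gives r/(n − k). The protocol supplies neither k nor r. Assume r = 2, k = 1 to 3, and measurable disease in everyone.

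| n | All treated | k = 1 | k = 2 | k = 3 |
|---|---|---|---|---|
| 18 | 2/18 = 11.1% | 2/17 = 11.8% | 2/16 = 12.5% | 2/15 = 13.3% |
| 9 | 2/9 = 22.2% | 2/8 = 25.0% | 2/7 = 28.6% | 2/6 = 33.3% |

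The rise is 0.7 to 2.2 points for n = 18 and 2.8 to 11.1 points for n = 9. With no responders, ORR is 0% on either denominator.

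**5. Effect on PFS at Day 43.** Assume the k subjects all die unscanned before Day 43 and nobody else has an event. All treated gives (n − k)/n; the Table 20 set gives 100%.

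| n | k = 1 | k = 2 | k = 3 | Table 20 set |
|---|---|---|---|---|
| 18 | 17/18 = 94.4% | 16/18 = 88.9% | 15/18 = 83.3% | 100% |
| 9 | 8/9 = 88.9% | 7/9 = 77.8% | 6/9 = 66.7% | 100% |

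**6. Is k = 1 to 3 reasonable?** The protocol gives no early death rate. Assume exponential survival with a median of m weeks, so P(death before week 6) = 1 − 2^(−6/m). For m = 16 this is 0.229; for m = 39 it is 0.101. Expected deaths are 18 × 0.229 = 4.1 down to 18 × 0.101 = 1.8, or 9 × 0.229 = 2.1 down to 9 × 0.101 = 0.9. Under these assumptions the figures are upper bounds on unscanned deaths in that window, since some of those who die would have had an end-of-treatment scan. They show that the range is not fanciful; they do not estimate it.

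**The case against.** A reader might infer that anyone who stops before the Cycle 3 scan disappears from the efficacy analysis. The schedule does not support that. An end-of-treatment scan is planned for every subject and a 3-month scan for many, and either one puts the subject in the set. This stands, and it narrows the point to subjects never scanned again. The safety net still has holes: the end-of-treatment measures are only those possible, the 3-month scan omits subjects who stopped for progression or new therapy, and no later scan recovers a death.

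A reader might also say that the protocol flatly contradicts itself. It does not quite. Section 7.7.1 defines a variable and Table 20 a population, and no sentence assigns PFS or ORR to a named set. A SAP could assign them to all treated subjects. But the table offers no other efficacy set, and Section 7.9 promises a SAP only if one is needed, so Table 20 may be the governing text.

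TTP is hardly touched, because death is not a TTP event. A living subject with no later scan would, under usual censoring (an assumption here), be censored at baseline and add nothing to a Kaplan-Meier curve. The PFS problem is therefore confined to unscanned deaths. Progression documented by a scan already brings the subject into the set.

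Finally, inclusion requires a life expectancy of at least 16 weeks and WHO performance status 0-2, so early deaths may be few. All data are listed by cohort, so a careful reader could find the omitted subjects. Both points limit the size, not the direction.

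**Conclusion.** The concern holds in limited form. If PFS and ORR are analysed on the tumour response set, which is a strong inference but not stated text, unscanned deaths are lost from PFS and never-rescanned subjects from the ORR denominator. PFS can shift only upward, and so can ORR whenever there is a responder.

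The size is unknown because the protocol gives no rate of unscanned subjects. The illustrations rest on an assumed 1 to 3 such subjects and 2 responders. On those assumptions the ORR shift is small at 18 treated and up to 11.1 points at 9, while the Day-43 PFS estimate loses 1 to 3 events altogether. A large, quantified inflation of median PFS might be tempting to claim, but nothing in the protocol supports one.

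Severity is low to moderate. Anti-tumour activity is a secondary, descriptive objective with no test, and neither the primary safety objective nor dose escalation uses this set.

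**What to change.** In Table 20, state that PFS is analysed on all treated subjects. State that ORR and best response use all treated subjects with measurable disease at baseline, with those lacking a post-baseline scan counted as non-responders and shown as not evaluable. The measurable-disease restriction follows Section 7.7, which summarises subjects with only non-measurable disease separately. Keep the scan-based set for percentage change in tumour size, where a post-baseline measurement is needed, and as a sensitivity analysis for ORR and PFS.

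The cost is one amended table row and a matching sentence in any SAP. The downside is a slightly lower reported ORR and PFS. Sample size and scan schedule stay as they are.
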